The goal of our investigation is to compare the efficacy of local administration of liposomal bupivacaine versus the efficacy of a peripheral nerve block in terms of post-operative pain scores after elective ankle and hindfoot surgery. We hypothesize that there will not be a significant difference in the pain scores of these two groups in opioid naïve patients. Furthermore, we aim to determine if there are differences in the amount of opioid medications utilized for post-operative pain control, patient satisfaction scores, functional outcomes, complications, and unscheduled healthcare contact between the two groups. In order to accomplish our goal and aims, we plan to conduct a randomized, controlled investigation.

Hypothesis and Aims:

Hypothesis:

We hypothesize that there will not be a significant difference in the pain scores of patients randomized into the liposomal bupivacaine group and the peripheral nerve block group in opioid naïve patients.

Specific Aim 1:

To compare post-operative pain scores after elective ankle and hindfoot surgery in patients who receive a local infiltration of liposomal bupivacaine versus a peripheral nerve block.

Specific Aim 2:

To compare opioid consumption in morphine equivalents after elective ankle and hindfoot surgery in the two groups.

Specific Aim 3:

To compare patient satisfaction scores after elective ankle and hindfoot surgery in the two groups.

Specific Aim 4:

To compare functional outcomes after elective ankle and hindfoot surgery in the two groups.

Specific Aim 5:

To compare complication rates after elective ankle and hindfoot surgery in the two groups.

Specific Aim 6:

To compare rates of unscheduled healthcare contact after elective ankle and hindfoot surgery in the two groups.

Study Design:

This is a prospective, randomized trial to investigate whether there is a difference in pain score, opioid consumption, patient satisfaction, functional outcomes, complication rates, and unscheduled healthcare contact associated with local liposomal bupivacaine infiltration versus peripheral nerve block in patient undergoing elective ankle and hindfoot surgery. Approximately 50 patients will be randomized.

Study Population:

Approximate Number of Subjects:

PI: [name]

IRB# 2018-0486

Version 1.1 (07/23/2019)

Approximately 50 total Geisinger patients will participate in the study.

Inclusion Criteria:

1. Patients 18 years of age or older

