c. Post-operative (At Discharge)

i. Oxycodone 5mg every 6 hours as needed for pain (30 tablets)

ii. Acetaminophen 500mg every 6 hours scheduled

2. Peripheral Nerve Block Group**a. Preoperative**

i. Peripheral Nerve Block performed by anesthesia team (blocks will be given by same anesthesia provider utilizing same technique every time in order to reduce variations in delivery of peripheral nerve block).

b. Intraoperative

i. No local analgesic agent infiltration

c. Post-operative (At Discharge)

i. Oxycodone 5mg every 6 hours as needed for pain (30 tablets)

ii. Acetaminophen 500mg every 6 hours scheduled

Patients will be randomized as to which analgesia regimen they will receive. The surgeon will not be blinded.

On the day that the patient is consented for the study, they will complete the following standard of care assessments in clinic:

1. VAS Pain Scale
2. Pain Catastrophizing Scale
3. PROMIS Self-Efficacy of Managing Symptoms

On the day of surgery, all qualifying patients will undergo their elective ankle or hindfoot surgery under standard practices. Randomized patients will receive pre-operative peripheral nerve block prior to the procedure. The participating surgeon will perform the procedure in accordance with their standard practice. Liposomal Bupivacaine will be injected prior to incision and after wound closure. Patients will

PI: [name]

IRB# 2018-0486

Version 1.1 (07/23/2019)

be placed in sterile dressings and a post-operative splint in accordance with the surgeon's standard practice. All patients will receive discharge instructions based on the surgeon's standard practice. All patients will receive the same post-operative opioid pain regimen.

Patients will keep a pain journal, documenting their pain from postoperative days 1-7. It will include pain score as well as pain medication utilization documentation starting from immediately in the Post-Anesthesia Care Unit, 6 hours post-op, and 12 hours post-op. Afterwards, participants will be asked to document pain score and pain medication utilization daily from post-operative days 1-7. They will bring their pain journal with them to their first postoperative visit.

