Patients will be seen at 2 weeks and 6 weeks postoperatively. During these visits, a routine wound check will be performed. The patient's range of motion and pain will be assessed. Any complications will be recorded. All postoperative care other than the medications prescribed at the time of discharge will be in accordance with each surgeon's standard practice. At each of these two visits, patients will complete the following assessments:

1. VAS Pain Scale
2. Pain Medication Utilization Questionnaire
3. Pain journal collection

At the conclusion of the 6-week post-operative period, the EMR will be reviewed and any instances of unscheduled healthcare contact (email, MyGeisinger messages, telephone calls, unscheduled clinic visits, ED visits) will be recorded and analyzed for cause.

All surgeons participating in the study will adhere to the randomization, treatment and follow-up protocol. There will be 2 participating sites within the Geisinger system (GMC and GMC Woodbine) whom will participate in this research project.

Study Time and Events Table

| Study Procedures | Visit ~pre-surgery | Visit Day of Surgery | 0, 6, & 12 Hours Post Op | Visit 2 week follow-up | Visit 6 week Follow-up |
|---|--------------------|----------------------|--------------------------|------------------------|------------------------|
| Office Visit | X | | | X | X |
| Prescreen | X | | | | |
| Provide Info Sheet | X | | | | |
| Review Inclusion/Exclusion | X | X | | | |
| Demographics, medical history, habits, historical diagnoses | X | | | | |
| Consent of Patient | X | | | | |
| Randomization | X | | | | |
| Outcome measures / examination assessment recorded | X | | X | X | X |
| Analgesia administration | | X | | | |
| Surgery | | X | | | |
| AE / Complication Reporting | | X | X | X | X |

Primary Endpoints:

The primary endpoint is to determine if there is a statistically significant difference in pain scores (VAS Pain Scale) for patients undergoing elective ankle and hindfoot surgery randomized to a group receiving intra-operative liposomal bupivacaine infiltration versus a group receiving a peripheral nerve block.

Secondary Endpoints:

1. Differences in morphine equivalents consumed for post-operative pain control
2. Difference in patient satisfaction score
3. Differences in functional outcomes
4. Difference in complications
5. Differences in unscheduled healthcare contact

Statistics:

PI: [name]

IRB# 2018-0486

Version 1.1 (07/23/2019)

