Statistical analysis will be performed by [name]

Data Management

Data to be Collected:

The following data will be collected from the EMR:

- PHI elements (will not be included in final dataset)
- Medical Record Number (MRN)
- Name
- Date of Birth
- Patient Demographics (Age, gender, weight, height, Body Mass Index (BMI))
- Medical History
- Narcotic use history
- Inflammatory or Rheumatoid Arthritis
- Complications / AE
- Wound Hematoma
- Superficial wound infection (defined as any prescription for post-op antibiotics)
- Wound complications
- Deep infection (defined as need for surgical irrigation and debridement)
- Crossover
- Number of patients randomized to liposomal bupivacaine group that request peripheral nerve block
- Unscheduled healthcare contact and reason for contact
- Phone calls
- Emails
- MyGeisinger Messages
- Unscheduled clinic visits
- ED visits
- Dates
- Date(s) and information related to admission, surgery, and discharge
- Date(s) and information related to clinic visits

The following data will be collected during the patient clinic visits:

- VAS Pain Scale (0-10)
- Pain journal from post-operative days 0-7 including pain medication utilization and pain scores

Data Collection and Storage

The data points outlined above will be reviewed and collected from the EMR by the study coordinator(s), project coordinator(s) and/or co-investigators. A data request will be submitted to the BC Data Broker, an independent person from the study team.

A member of the IRB-approved Geisinger study team will perform a manual chart review for data points not captured during the BC data pull. A member of the IRB approved study team will randomly assign

PI: [name]

IRB# 2018-0486

Version 1.1 (07/23/2019)

study ID numbers in order to protect the identity of the subject. After the dataset has been de-identified, an IRB-approved study team member will forward the completed dataset to [name] for analysis. All study data will be kept in GHS maintained username/password-protected computer files and hard copy data will be double locked and accessible only to the study investigators in the locked office of the Study Coordinator. Only group-level information without personal identifiers will be included when presenting results or submitting manuscripts for publication.

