Personal or sensitive information that could be potentially damaging to participants (e.g. relating to illegal behaviors, alcohol or drug use, sexual attitudes, mental health, etc.) will not be collected. With concerns to HIV/AIDS status, if the status is already in the participant's medical record it will be reported into the CRF as a "yes" or "no," otherwise it will be reported in the CRF as "not assessed." Regarding collected mental health information that could be potentially damaging to participants, participants indicating that they are very depressed, thus raising concern regarding their mental state, will be referred to their primary care physician.

No PHI will be shared outside of the IRB approved study staff.

Records Retention

Records of data generated in the course of the study will be kept indefinitely and may be used for future research purposes.

Adverse Event Reporting

Clinical adverse events (AEs) will be monitored throughout the study. All AEs will be reported to the institutional review board (IRB) according to IRB policy. The date and time of onset and outcome, course, intensity, action taken, and causality to study treatment will be assessed by the study PI.

Definitions

An adverse event (AE) is any untoward, undesired, or unplanned event in the form of signs, symptoms, disease, or laboratory or physiologic observations occurring in a person given a test article or in a clinical study. The event does not need to be causally related to the test article or clinical study.

Adverse Events related to Elective Ankle and Hindfoot Surgery:

- Infection
- Wound healing issues
- Persistent pain
- Peripheral nerve injury
- Arterial injury
- Wound complications

A protocol-related adverse event is an AE occurring during a clinical study that is not related to the test article, but is considered by the investigator or the medical monitor (or designee) to be related to the research conditions, i.e., related to the fact that a subject is participating in the study. For example, a

protocol-related AE may be an untoward event occurring during a washout period or an event related to a medical procedure required by the protocol.

Recording and Reporting

A subject's AEs will be recorded and reported from the signing of the informed consent form to end of study period.

Protection of human subjects

Informed Consent

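### Reasons for unscheduled contact and two undefined wound items are coded from the chart with no separation from arm-revealing information

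*Protocol*

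**What the plan says.** - **Contacts.** Under Procedures, the record is reviewed after the six-week period, and the unscheduled contacts found "will be recorded and analyzed for cause". Data to be Collected lists the reason for contact as an item.
- **Who abstracts.** Under Data Collection and Storage, the listed data points "will be reviewed and collected from the EMR by the study coordinator(s), project coordinator(s) and/or co-investigators". For what the data pull misses, a study-team member will "perform a manual chart review for data points not captured during the BC data pull".
- **Independent step.** The same section states: "A data request will be submitted to the BC Data Broker, an independent person from the study team". The broker's stated task is the data request only.
- **Arm-revealing items.** The list taken from the record includes information on the surgery, and a crossover item: "Number of patients randomized to liposomal bupivacaine group that request peripheral nerve block".
- **Wound items.** Superficial infection is defined by an antibiotic prescription and deep infection by a surgical washout. Wound hematoma and wound complications have no criteria.
- **Blinding.** Procedures states: "The surgeon will not be blinded". The Protocol is silent on coordinators and chart reviewers. Study ID numbers are assigned for privacy and are not described as masking.
- **Endpoints.** Complications and unscheduled contact are the fourth and fifth secondary endpoints and the subjects of Specific Aims 5 and 6.

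**The concern.** Deciding why a patient telephoned or sent a message, or whether a wound note amounts to a complication, takes judgement. In a comparison of two analgesic techniques, whether a contact was about pain is the judgement most open to the reader's expectations. The Protocol gives these judgements to study staff in the same abstraction exercise that collects surgery information and an item defined by randomized arm. If the coder knows the arm, a borderline contact or wound note can be classified differently in the two groups, and no later analysis can undo that. Coding can be masked even where treatment is open, and the plan already has a person independent of the team who could supply masked extracts.

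**Working it through.** The plan gives no figure for this point, so there is nothing to reproduce. The check has two parts.

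**1. Which items need judgement, and is the arm kept away from them?**

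| Item | Discretion for a chart coder | Stated endpoint? |
|---|---|---|
| Reason for contact | High: no categories given | No. Collected and analysed, but the endpoint and Aim 6 concern contact itself and its rate |
| Count of contacts | Low: logged events of listed types | Yes |
| Wound hematoma, wound complications | Some: no criteria given | Yes, as part of complications |
| Superficial and deep infection | Little: each tied to a recorded action | Yes, as part of complications |
| AE causality | High, assessed by the PI | No |
| VAS pain | None: patient-reported | Primary |

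The reason for contact and the two undefined wound items remain. For these, no section orders the work so that coding precedes knowledge of the arm. That the chart shows the arm is an inference: one arm has a block by the anesthesia team and the other an infiltration in surgery, and either would normally be charted. The Protocol does not say so.

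**2. What could arm-dependent coding do? (illustration only)**

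The one input from the documents is the sample size: "Approximately 50 patients will be randomized". All others are assumed: 25 per arm, a two-sided 5% test, no true difference, and the rates below.

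*Wound items, per patient.* With true rate p and detection s1 and s2 by arm, the false difference is p × (s1 − s2). Rejection rates come from exact enumeration of two binomials with 25 patients each.

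- p = 0.30, 90% detection in both arms: difference 0. Rejection is 2.2% (Fisher) and 5.4% (chi-square).
- p = 0.30, 90% against 70%: 0.30 × 0.20 = 0.06, and 25 × 0.06 = 1.5 patients. Rejection is 3.8% and 8.4%.
- p = 0.30, 95% against 60%: 0.30 × 0.35 = 0.105, or 2.6 patients. Rejection is 7.7% and 14.9%.
- p from 0.20 to 0.40, 90% against 70%: false difference 4 to 8 points. Rejection is 2.9% to 5.1% (Fisher) and 7.2% to 9.9% (chi-square).

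*Contact cause, per contact.* Assume n contacts per arm, 40% truly pain-related, and a coding drift d in one arm. Then SE = √[(0.40 × 0.60 + (0.40 + d)(0.60 − d)) / n], and the chance of a significant result is Φ(d/SE − 1.96) + Φ(−d/SE − 1.96).

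- n = 50 (2 contacts per patient), d = 0.10: SE = √[(0.24 + 0.25)/50] = 0.0990, d/SE = 1.01, chance 17.3%.
- n = 50, d = 0.15: SE = √[(0.24 + 0.2475)/50] = 0.0987, d/SE = 1.52, chance 33.0%.
- n = 25, d = 0.05: chance 6.5%.
- n = 75, d = 0.15: chance 46.0%.

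This second set treats contacts as independent, although they cluster within patients. An analysis that respects the clustering would flag the same drift less often. The 6.5% to 46.0% spread reflects the assumptions more than the trial.

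**The case against.** The strongest reply is that little here is both subjective and an endpoint. Contacts are mostly logged events, the endpoint and Aim 6 concern rates of contact, and cause is only a descriptor. Two of the wound items follow fixed rules, and for the other two a written definition would help more directly than masking. The assumed drifts have no source, and the only stated expectation is of no difference in pain scores. Category lists and arm labels in the analysis file may also sit in an analysis plan that is not shown. Most of this stands and sets the scope of the point. What remains is that the Protocol itself says cause will be analysed and itself fixes who reads the chart. The order in which records are read is study conduct, which an analysis plan cannot repair afterwards.

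A reader might infer more than the text supports:

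- **AE causality as a biased endpoint.** The Protocol says "causality to study treatment will be assessed by the study PI", but this stands under adverse event reporting and is not a listed endpoint. Judging causality to a treatment ordinarily requires knowing the treatment.
- **That the abstractor must know the arm.** The crossover item is a count for one arm. Block requests could be abstracted for every patient and the arm merged later, or another listed person could do it. The text allows knowledge of the arm but does not require it.
- **That all complications are judged from charts.** They are also recorded at the two- and six-week visits, and part of the record data comes through the broker.
- **That the primary result is affected.** The VAS score is reported by the patient and is not coded from the chart.

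**Conclusion.** The point holds in limited form. The reason for contact and the items wound hematoma and wound complications are abstracted by study staff, possibly co-investigators, with no step that separates this coding from arm-revealing information. Arm-dependent coding is therefore possible. It is not shown to be likely, and its size cannot be derived from the documents. The figures above show only that, at about 25 per arm, a false difference of one to three patients is conceivable for a wound item, and that tests on contact cause could be disturbed by a modest drift. They rest on assumed allocation, event rates, detection rates and drifts. The consequence is confined to one secondary endpoint component and to one descriptor that the trial says it will analyse. This is a cheap improvement and does not call the trial's main comparison into question.

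**What to change.** Add one paragraph to Procedures and to Data Collection and Storage:

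1. The data broker exports contact texts and wound notes under study ID, without the arm, operative record or anesthesia record.
2. An already listed coordinator who did not handle that patient's randomization or surgery, where one is available, codes the reason for contact and the two wound items from a fixed list with written definitions.
3. The codes are locked. Only then is the arm merged and the crossover item abstracted.
4. Texts that reveal the arm are flagged, so that the coding can be examined with and without them.

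The cost is some extra export work for the broker and a short list of definitions; no new assessor is needed. Masking will be imperfect where a patient or clinician mentions the block. The change does nothing for complications recorded at visits by unblinded surgeons, and the Protocol should state that as a limitation.

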2. Patients undergoing elective primary ankle or hindfoot surgery (ankle arthrodesis, subtalar arthrodesis, triple arthrodesis, total ankle arthroplasty, peroneal tendon debridement/transfer, Cavus Reconstruction, Medial Displacement Calcaneal Osteotomy, Dwyer Osteotomy)

Exclusion Criteria:

1. Patients who are undergoing revision surgical procedure
2. Patients who have taken opioid pain medications in the past 3 months prior to surgical procedure
3. Patients who have allergies to any of the medications or components of medications investigated in the study
4. Patients currently incarcerated
5. Patients who cannot read and speak English

Study Recruitment:

The study investigators will identify potential study participants in the outpatient clinic. The patients that meet inclusion criteria will be approached by the physician investigator, research coordinator(s), and/or research assistant(s) during their orthopaedic clinic visit and will be asked to participate in the study. After hearing the study explanation, if the patient is interested in participating, the physician investigators, research coordinator(s) and/or research assistant(s) will review, with the patient, the informed consent form asking authorization to access/use their PHI. The patient will sign and date the form after all questions have been satisfactorily answered by the study team. Recruitment materials will consist of the informed consent form.

Study Duration:

Approximate Duration of Subject Participation:

Patients will participate in the study for approximately 3 months – from initial recruitment to end of participation.

Approximate Duration of Study:

The study will be completed in approximately 12 months. The end of the study is the last visit of the last subject, or end of collection of data from the patient's electronic health record.

Procedures:

Patients who meet inclusion criteria will undergo a selection process, and if they choose to participate will be randomized into one of two groups. The randomization scheme will be created with the use of an internet based randomization website (<https://www.randomizer.org>). Qualifying subjects will be randomized into one of two groups prior to their surgery:

PI: [name]

IRB# 2018-0486

Version 1.1 (07/23/2019)

1. Liposomal Bupivacaine Group**a. Pre-operative**

i. No peripheral nerve block will be given

b. Intraoperative

i. Local infiltration of 20cc of Liposomal Bupivacaine infiltrated to the surgical area

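### Is it a flaw that patients are randomised at the clinic visit, before eligibility is reviewed again on the day of surgery?

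*Protocol*

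**What the plan says.** In the Study Time and Events Table the eligibility row reads "Review Inclusion/Exclusion | X | X": once at the pre-surgery visit, once on the day of surgery. The randomisation row reads "Randomization | X", at the pre-surgery visit only. The treatment row reads "Analgesia administration | | X", on the day of surgery.

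Under Procedures the text says "Qualifying subjects will be randomized into one of two groups prior to their surgery". On method it says "The randomization scheme will be created with the use of an internet based randomization website", and it does not describe how the next allocation is released. It also says that the surgeon is not blinded.

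Exclusion criterion 2 is "Patients who have taken opioid pain medications in the past 3 months prior to surgical procedure". The Hypothesis compares pain scores of patients "randomized into the liposomal bupivacaine group and the peripheral nerve block group in opioid" naïve patients. The protocol does not say what happens to a randomised patient who fails the second review, who carries out that review, or whether that person knows the arm.

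**The concern.** The opioid criterion runs up to the operation, so it cannot be settled finally in clinic. The protocol therefore schedules a check that can fail after the arm has been assigned. If such patients were dropped by someone who knows the arm, the exclusions could differ between arms and distort the pain comparison. If they were kept, the analysed group would no longer be strictly the opioid-naïve population of the Hypothesis. Randomising after the second review, with the next allocation hidden, would avoid both. At stake would be the comparability of two arms of about 25 patients.

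**Working it through.** **Consistency.** The table puts randomisation at the clinic visit and the text puts it before surgery. The first is a case of the second, so there is no contradiction. Nothing in the protocol says that patients failing the second review are removed.

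**How many patients.** The interval between visit and surgery is not stated. Study Duration says "Patients will participate in the study for approximately 3 months". Reading that as 2.5, 3 or 3.5 months (10.9, 13.0 or 15.2 weeks) and subtracting the 6 weeks of follow-up leaves 4.9, 7.0 or 9.2 weeks, or less if part of the period falls after the 6-week visit. The share taking an opioid in that time is not given. I assume 2%, 5% or 10%.

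- Expected late-ineligible patients: 50 × 0.02, 0.05, 0.10 = 1, 2.5, 5, or 0.5, 1.25, 2.5 per arm of 25 (1:1 is assumed).
- These counts measure ineligibility, not bias. Removal that does not depend on the arm causes no bias.

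**Size of bias if removal were as lopsided as possible.** Assumptions: 25 per arm, no true effect, outcome SD 1, a predictor of exposure correlated ρ = 0.3 or 0.5 with pain, all exposed patients removed from one arm and none from the other, pooled t-test at two-sided 0.05. Each cell is 400,000 simulated trials (Monte Carlo standard error 0.0003). Without removal the rate was 0.0496 to 0.0504.

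| Selection | ρ | False-positive rate at 2% / 5% / 10% | Shift in SD at 2% / 5% / 10% |
|---|---|---|---|
| Moderate (odds of exposure double per SD of predictor) | 0.3 | 0.0502 / 0.0496 / 0.0504 | 0.004 / 0.010 / 0.020 |
| Moderate | 0.5 | 0.0507 / 0.0504 / 0.0516 | 0.007 / 0.017 / 0.033 |
| Extreme (exposed are exactly those highest on the predictor) | 0.3 | 0.0503 / 0.0508 / 0.0548 | 0.015 / 0.032 / 0.059 |
| Extreme | 0.5 | 0.0510 / 0.0535 / 0.0624 | 0.025 / 0.054 / 0.098 |

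The extreme shifts can be checked by formula. Removing the top share p of a normal predictor lowers the mean outcome by ρ·φ(z)/(1 − p), where z is the cut-off. For p = 0.10 and ρ = 0.5: 0.5 × 0.1755/0.90 = 0.098, as simulated.

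The standard error of the difference is √(2/25) = 0.283 SD. The largest moderate shift is 0.033/0.283 = 12% of that; the smallest is 0.004/0.283 = 1%. With an assumed pain-score SD of 2.5 points, 0.033 SD is 0.08 points, and the extreme 0.098 SD is 0.245 points. Four of the six moderate false-positive rates lie within the no-removal range.

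**Is moving randomisation the only remedy?** No. There are three ways to handle a late-ineligible patient:

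1. Remove with the arm known: open to selection.
2. Keep everyone randomised: no selection, slight departure from the opioid-naïve population.
3. Remove by a fixed rule on opioid use before treatment, applied by someone who does not know the arm: no selection, population kept.

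The third uses information the protocol already plans to take from the electronic record, since Data to be Collected includes the history of narcotic use. Such a rule is normally set in the statistical analysis plan, which was not available here.

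**What the move would cost.** The Peripheral Nerve Block Group section requires the same anaesthesia provider for every block, and Procedures names two sites. If the arm is known only on the day, that provider must be available for every case. At 1:1, 50 × 0.5 = 25 of those cases would need no block. Early allocation lets block cases be scheduled around the provider.

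**The case for a change.** The strongest argument is that the order of steps is protocol conduct: an analysis plan can decide whom to analyse but cannot change when patients were randomised. The situation is also likely to arise. With 50 patients, the chance of at least one late-ineligible patient is 1 − 0.98^50 = 64% at 2% exposure and 1 − 0.95^50 = 92% at 5%. Both regimens start on the day of surgery, and randomising that day would still fit the text. All of this is true. It shows that later randomisation is possible and tidy, not that the present order is wrong: the order need not be undone if late ineligibility can be handled without bias.

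A harsher calculation is possible. If 20% of one arm (5 of 25) were removed and their pain was 1 SD above the rest, the shift would be 0.20 × 1 = 0.20 SD against a standard error of √(1/25 + 1/20) = 0.30, and the false-positive rate would be about 10.2%. But five or more exposed patients in one arm has probability 0.01%, 0.7% or 9.8% at the three assumed rates, and all of them would then have to be removed with none removed from the other arm.

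Some loss of precision stands. If late removal left 45 of 50 patients, power for the 0.79 SD difference detectable with 25 per arm (two-sided 0.05) would fall from 80% to 76%. Analysing everyone randomised avoids that.

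The silence on concealment of the next allocation is unstated detail, not evidence of an open list. It matters for this point only as a condition of the later randomisation: without it, moving the table mark would not achieve its purpose.

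**Conclusion.** The concern does not hold. The table is read correctly, but the protocol neither contradicts itself nor prescribes a biased exclusion, and it does not say that the person reviewing eligibility knows the arm. The potential harm is close to nil under moderate selection (false-positive rate 5.0% to 5.2%, shift at most 0.033 SD). It reaches 6.2% and 0.10 SD only if 10% are exposed, exposure falls exactly on the highest-predictor patients, and removal is confined to one arm. Against this stands a practical burden on the single block provider at two sites. Choosing between the two orders is a reasonable trade-off for the sponsor.

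This rests on assumed figures for exposure, correlation, pain-score SD and allocation ratio, none of which the protocol gives. It also assumes that knowing the arm does not itself change whether a patient takes an opioid before surgery.
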